$$SD_b = \sqrt{\frac{\sum_{j=1}^m \left(\overline{BG_j} - \frac{\sum_{j=1}^m \overline{BG_j}}{m}\right)^2}{m-1}}$$

- Calculated as glucose coefficient of variation (CV):
 - Within-day $CV(CV_w)$

Each participant should have one CV_w per CGM session. CV_w is calculated by calculating the CV individually on all valid days withing a CGM session and then averaging those CVs across all days in the session:

$$CV_w = \frac{\sum_{j=1}^m CV_j}{m}$$

where m stands for the number of valid CGM days in a session and

$$CV_j = \frac{SD_j}{\overline{BG_j}} \times 100$$

• Between-day $CV(CV_b)$

Each participant should have one CV_b per CGM session. CV_b is calculated by averaging the glucose values individually on each valid day within a session and then calculating the CV across those days:

$$CV_b = \left| \frac{SD_b}{\underline{\sum_{j=1}^m \overline{BG_j}}} \right| \times 100$$

- TITR Time in Tight Target Range (71 to 140 mg/dL or 3.9 to 7.8 mmol/L)
 - Calculated as percentage of time per day in tight target range:
 - Percentage of time in tight target range for a given day will be calculated as 100 times the number of CGM data readings where a participant's blood glucose falls within the specified range during a day (00:00 to 23:59, inclusive), divided by the total number of readings in the time interval (00:00 to 23:59, inclusive). This will be averaged over the days from Day 1 to Day 14 to obtain TITR for a participant at a visit.
- Composite of all in ranges
 - Composite endpoint of the recommended time in all three International CGM Consensus Guidelines ranges (<4% in TBR [≤70 mg/dL], >70% in TIR, and <25% in TAR [>180 mg/dL]):

- A binary endpoint will be created. If for a participant at a visit all three CGM measures (TAR, TIR, TBR) are within the recommended time-ranges then the composite endpoint will be set to "Y" for that participant, otherwise it will be set to "N".
- Mean 24-hr daily blood glucose

Calculated by averaging all non-missing glucose readings a day (00:00 to 23:59, inclusive) and averaging across the 14 days to obtain mean daily glucose for a participant at a visit.

• Fasting glucose and post-prandial glucose excursion

Both the endpoints are algorithmically derived from the entire CGM dataset. An algorithm reviews the entire CGM dataset, evaluates excursions, and time periods then estimates either the fasting glucose or post-prandial glucose excursion.

Summary statistics will be provided for actual values by visit (Baseline, Week 4, and Week 12) and changes from baseline values by each post-baseline visit (Week 4 and Week 12). The odds for a subject to reach a composite endpoint of the recommended time in all three International CGM Consensus Guideline ranges will be compared between baseline and Week 12 by a logistic regression model. The model will also include, baseline HbA1c ($\leq 8.0\%$, > 8.0%), and baseline composite endpoint as fixed effect.

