When count data are presented, the percentage will be suppressed when the count is zero in order to draw attention to the non-zero counts. A row denoted "Missing" will be included in count tabulations where specified on the shells to account for dropouts and missing values. The denominator for all percentages will be the number of subjects in that treatment within the analysis set of interest, unless otherwise specified.

The analysis model to make comparisons within treatment relative to continuous measurements assessed over time will be an MMRM with terms for:

- Visits, as fixed effects
- Baseline HbA1c ($\leq 8.0\%$, > 8.0%), as a covariate
- Baseline measurement, as a covariate

For analyses of HbA1c, continuous baseline HbA1c will be included in the model instead of baseline HbA1c category. An unstructured covariance structure will model the relationship of within-participant errors.

Logistic regression may be used to examine the within-treatment effect from baseline at 12 weeks in binary efficacy outcomes. The negative binomial regression model will be used to measure the within-treatment effect of discrete count measures if deemed appropriate.

Summary of intercurrent events:

The number of participants who experience an intercurrent event will be summarized in a table by event type (treatment discontinuation for any reason, or initiation of prohibited medication) and visit. For each visit, the number of intercurrent events which happened before or during the measurements taken on that visit will be calculated, excluding the events which happened during or before the measurements taken at the previous visits.

Furthermore, the number of participants without any intercurrent events will be presented by visit too. At each visit the number and percentage of participants without intercurrent events will be shown.

All analyses will be conducted using SAS Version 9.4 or higher.

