4.5.1. Summary for the Analysis of Exploratory Measures

Objective	Relative to the efficacy measure	Analysis Conducted	Additional information
CGM parameters	Mean change in	MMRM model as	MMRM with terms for:
	TIR from baseline	specified in Section 4.3.2	• Visit
			• Baseline HbA1c category (≤8.0%, >8.0%), and
			• Baseline TIR as a covariate
CGM parameters	Mean change in	MMRM model as	MMRM with terms for:
	TBR from baseline at week 12	specified in Section 4.3.2.	• Visit
			• Baseline HbA1c category (≤8.0%, >8.0%), and
			• Baseline TBR as a covariate
CGM parameters	Mean change in TITR from baseline at week 12	MMRM model as specified in Section 4.3.2 .	MMRM with terms for:
			• Visit
			• Baseline HbA1c category (≤8.0%, >8.0%), and
			• Baseline TITR as a covariate
CGM parameters	ters Mean change in GV MMRM model as specified in		Separate MMRM model for all measures of GV.
	week 12	Section 4.3.2.	MMRM with terms for:
			• Visit
			• Baseline HbA1c category (≤8.0%, >8.0%), and
			• Baseline GV measure as a covariate
CGM parameters	Change in odds for reaching composite	Logistic regression model as specified	Logistic Regression with terms for:
	endpoint of all in ranges from baseline to week 12	in Section 4.5	• Visit

Table 3.	Exploratory measures not controlled for Type 1 error
----------	--

			 Baseline HbA1c category (≤8.0%, >8.0%), and Baseline composite endpoint as a covariate
CGM parameters	Mean change in mean 24-hr daily blood glucose from baseline at week 12	MMRM model as specified in Section 4.3.2.	 MMRM with terms for: Visit Baseline HbA1c category (≤8.0%, >8.0%), and Baseline mean 24-hr daily blood glucose as a covariate
CGM parameters	Mean change in estimated post- prandial glucose excursion from baseline at week 12	MMRM model as specified in Section 4.3.2.	 MMRM with terms for: Visit Baseline HbA1c category (≤8.0%, >8.0%), and Baseline estimated post-prandial glucose excursion as a covariate
CGM parameters	Mean change in estimated fasting glucose at week 12	MMRM model as specified in Section 4.3.2.	 MMRM with terms for: Visit Baseline HbA1c category (≤8.0%, >8.0%), and Baseline estimated fasting glucose as a covariate

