4.9. Changes to Protocol-Planned Analyses

There are no changes to protocol planned analyses.

5. Sample Size Determination

A sample size of 150 participants will provide at least 90% power to show an improvement in HbA1c from baseline at Week 12. This sample size is using the following assumptions:

- a 1-sample t-test with 2-sided significance level of 0.05
- within treatment difference from baseline at Week 12 is 0.3%, and
- intra-subject variability of 1.1%.

6. Supporting Documentation

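### The logistic model for the CGM composite compares baseline with Week 12 while also adjusting for the baseline composite, so its visit odds ratio measures neither the marginal nor the paired change

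*SAP*

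**What the plan says.** SAP 4.5 defines the composite per participant and visit as Y or N: "A binary endpoint will be created", set to Y when time below, in and above range all meet the recommended limits. The odds of Y "will be compared between baseline and Week 12 by a logistic regression model". The same paragraph adds baseline HbA1c category and "baseline composite endpoint as fixed effect".

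The Table 3 row in SAP 4.5.1 agrees. Its target is the change in odds for reaching the composite "endpoint of all in ranges from baseline to week 12". Its terms are visit, baseline HbA1c category and "Baseline composite endpoint as a covariate". The table is headed "Exploratory measures not controlled for Type 1 error".

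The only other provision is the general one in SAP 4.1: "Logistic regression may be used to examine the within-treatment effect from baseline at 12 weeks in binary efficacy outcomes". None of these places says which visits supply outcome rows, whether the odds ratio is marginal or within-participant, or how two or more records from one participant are handled.

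**The concern.** A baseline covariate belongs in the MMRMs of SAP 4.3.2 and Table 3 because their outcome is a change measured at post-baseline visits only. Here the stated comparison makes baseline one of the two outcome levels. On every baseline row the covariate then equals the outcome; on Week 12 rows it does not. The model has no visit-by-baseline term to absorb that difference. It fits a very large common effect for the baseline composite, and the visit coefficient is pushed away from zero to compensate.

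At stake is how one exploratory result is read. The composite is the only binary efficacy endpoint listed. An odds ratio labelled as the change from baseline to Week 12 would overstate that change on either usual scale.

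**Working it through.** **The plan's own figure.** No rate, effect or power is given for the composite. The only design figure is for HbA1c: "A sample size of 150 participants will provide at least 90% power to show an improvement in HbA1c from baseline at Week 12" (SAP section 5). With difference 0.3, SD 1.1 and n = 150, the noncentrality is 0.3 / (1.1/√150) = 3.34, and two-sided one-sample t-test power at 0.05 is 0.913. It reproduces and does not bear on this point.

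**Possible outcome rows.**
- Baseline and Week 12: Visit gives the stated contrast, but the baseline outcome is its own covariate.
- Weeks 4 and 12: the covariate is proper, but Visit contrasts Week 4 with Week 12.
- Week 12 only: Visit has one level and cannot be estimated.

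**Literal model, large-sample fit.** Let X be the baseline composite, V = 0 at baseline and 1 at Week 12, and logit P(Y=1) = a + bV + cX. HbA1c category is left out here. With p0 and p1 the proportions at the two visits, p11 the proportion Y at both, and f(X,V) the fitted probabilities, the likelihood equations are:
- (1−p0)·f(0,0) + p0·f(1,0) = p0
- (1−p0)·f(0,1) + p0·f(1,1) = p1
- p0·[f(1,0) + f(1,1)] = p0 + p11

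The log odds difference between visits must be the same at X = 0 and X = 1.

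**Worked example (assumed rates).** 40% are Y at baseline; at Week 12, 80% of those and 30% of the others are Y. Then p11 = 0.4 × 0.8 = 0.32, the N-to-Y cell is 0.6 × 0.3 = 0.18, the Y-to-N cell is 0.08, and p1 = 0.50.
- Marginal OR = (0.5/0.5)/(0.4/0.6) = 1.50
- Paired OR = 0.18/0.08 = 2.25

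| Row | Observed proportion Y | Fitted |
|---|---|---|
| Baseline, X = 0 | 0 | 0.093 |
| Baseline, X = 1 | 1 | 0.860 |
| Week 12, X = 0 | 0.30 | 0.207 |
| Week 12, X = 1 | 0.80 | 0.940 |

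Check: 0.6 × 0.0932 + 0.4 × 0.8602 = 0.40; 0.6 × 0.2068 + 0.4 × 0.9398 = 0.50; 0.4 × (0.8602 + 0.9398) = 0.72 = 0.40 + 0.32.

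Visit OR = (0.9398/0.0602)/(0.8602/0.1398) = 2.54. That is 1.69 times the marginal and 1.13 times the paired OR. The model fits neither visit: it must compromise between rows where X determines Y and rows where it does not.

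A larger assumed gain: 40% to 66%, with 90% and 50% responding at Week 12. Marginal OR = (0.66/0.34)/(0.4/0.6) = 2.91; paired OR = 0.30/0.04 = 7.5; visit OR = 12.0.

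**Range.** Joint tables came from a bivariate-normal threshold model with baseline rates of 20% to 60% and latent correlation 0.3 to 0.7, all assumed:

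| Gain | Visit OR ÷ marginal OR | Visit OR ÷ paired OR |
|---|---|---|
| 0 points | 1.00 | 1.00 |
| 10 points | 1.25–1.81 | 1.12–1.18 |
| 20 points | 1.58–4.37 | 1.27–1.75 |
| 30 points | 2.05–19.5 | 1.49–3.81 |

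The top of the last row comes from 60% rising to 90%; excluding that pair of rates, the highest ratio to the marginal OR is 8.95. The odds ratio for the baseline composite itself runs from about 16 to over 2000, which is the self-prediction.

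**With HbA1c category, N = 150, 1000 runs per scenario, latent correlation 0.5.** Median visit OR was 2.12 for 40% to 50% (1.57 with the baseline composite dropped; paired 1.83), and 4.69 for 40% to 60% (2.45 and 3.35). Including HbA1c category does not remove the effect.

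**Correlation.** In three no-change scenarios the median OR was 1.0. At nominal 5%, the model with rows treated as independent rejected in 7.3% to 8.9% of runs, against 3.9% to 5.3% with errors clustered on participant and 5.2% to 6.2% for McNemar's test. The Monte Carlo standard error is √(0.05 × 0.95/1000) = 0.7 points.

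**The case against.** The strongest reply is that the composite row simply follows the Table 3 template of visit, HbA1c category and baseline value, whose models use post-baseline visits only. Read so, nothing predicts itself. That stands as a possible reading, but it does not rescue the plan: Visit would then contrast Week 4 with Week 12, while both the text and the table ask for baseline against Week 12.

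A reader might infer that the odds ratio is inflated several-fold as a general matter. The documents do not support that. They give no response rates; there is no distortion without a change; and ratios of that order need gains of about 20 to 30 points or high within-participant correlation. They also take the marginal OR as the only right answer. SAP 4.5 speaks of the odds for a subject, which is compatible with a within-participant OR. Against that target the excess is much smaller, so much of the gap to the marginal OR is the ordinary difference between conditional and marginal odds ratios.

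Nor is the model the only information on how many participants reach the ranges. SAP 4.5 plans summaries at baseline, Week 4 and Week 12, and SAP 4.1 describes categorical data by count and percentage, so observed proportions would stand beside the odds ratio. Finally, the SAP is silent on correlation rather than specifying independence; the excess rejection applies only if rows are analysed as independent.

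**Conclusion.** The specification is wrong as written: no choice of outcome rows lets the stated model validly estimate the stated comparison. Under the literal reading the visit OR moves away from 1 whenever the proportion changes, by an amount set by the gain and the within-participant correlation. The sizes are conditional on assumed rates and the threshold model.

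The consequence is limited. The direction of effect is preserved, the analysis is exploratory without type I error control, and the HbA1c test, the secondary endpoints and the sample size do not depend on it. Inferring that the trial's main conclusions are at risk would go beyond the documents.

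**What to change.** Remove the baseline composite from this model in SAP 4.5 and in the Table 3 composite row. Compare baseline with Week 12 as paired binary outcomes in participants with compliant CGM sessions at both times, by one of:
- a GEE logistic model with visit (baseline, Week 12) and baseline HbA1c category, with robust errors clustered on participant, reporting a population-averaged odds ratio; or
- the paired difference in proportions with 95% CI and McNemar's test.

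State in both places which target, marginal or paired, is reported, since the two odds ratios differ even when both are computed correctly. If the sponsor prefers to keep the baseline composite as a covariate, restrict outcome rows to post-baseline visits and stop describing the result as a change in odds from baseline.

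The cost is a few words in SAP 4.5, one table row and a few lines of code. No new data are needed.

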4.5.1. Summary for the Analysis of Exploratory Measures

Objective	Relative to the efficacy measure	Analysis Conducted	Additional information
CGM parameters	Mean change in	MMRM model as	MMRM with terms for:
	TIR from baseline	specified in Section 4.3.2	• Visit
			• Baseline HbA1c category (≤8.0%, >8.0%), and
			• Baseline TIR as a covariate
CGM parameters	Mean change in	MMRM model as	MMRM with terms for:
	TBR from baseline at week 12	specified in Section 4.3.2.	• Visit
			• Baseline HbA1c category (≤8.0%, >8.0%), and
			• Baseline TBR as a covariate
CGM parameters	Mean change in TITR from baseline at week 12	MMRM model as specified in Section 4.3.2 .	MMRM with terms for:
			• Visit
			• Baseline HbA1c category (≤8.0%, >8.0%), and
			• Baseline TITR as a covariate
CGM parameters	ters Mean change in GV MMRM model as specified in		Separate MMRM model for all measures of GV.
	week 12	Section 4.3.2.	MMRM with terms for:
			• Visit
			• Baseline HbA1c category (≤8.0%, >8.0%), and
			• Baseline GV measure as a covariate
CGM parameters	Change in odds for reaching composite	Logistic regression model as specified	Logistic Regression with terms for:
	endpoint of all in ranges from baseline to week 12	in Section 4.5	• Visit

Table 3.	Exploratory measures not controlled for Type 1 error
----------	--

			 Baseline HbA1c category (≤8.0%, >8.0%), and Baseline composite endpoint as a covariate
CGM parameters	Mean change in mean 24-hr daily blood glucose from baseline at week 12	MMRM model as specified in Section 4.3.2.	 MMRM with terms for: Visit Baseline HbA1c category (≤8.0%, >8.0%), and Baseline mean 24-hr daily blood glucose as a covariate
CGM parameters	Mean change in estimated post- prandial glucose excursion from baseline at week 12	MMRM model as specified in Section 4.3.2.	 MMRM with terms for: Visit Baseline HbA1c category (≤8.0%, >8.0%), and Baseline estimated post-prandial glucose excursion as a covariate
CGM parameters	Mean change in estimated fasting glucose at week 12	MMRM model as specified in Section 4.3.2.	 MMRM with terms for: Visit Baseline HbA1c category (≤8.0%, >8.0%), and Baseline estimated fasting glucose as a covariate

4.6. Safety Analyses

Safety assessments will be done using the Safety Analysis Set (SS) irrespective of adherence to study intervention or initiation of prohibited medication, unless indicated otherwise.

4.6.1. Extent of Exposure

Duration of exposure is defined as the total number of days a subject is exposed to any study intervention and will be presented as the total number of days from the first dose date (Day 1) to the last dose date (date of last dose minus the date of first dose + 1) as recorded on the Disposition Event: Treatment / Dosing pages on the CRF. If the last dose date on Disposition Event: Treatment / Dosing pages is missing, or if a participant is lost to follow-up, but the drug accountability log confirms that the participant has taken study drug, the visit date following the last completed drug accountability log will be used.

Missing doses will be ignored in this calculation.

The duration of exposure to study intervention will be summarized for all participants in the SS and will be presented in a table by summary statistics. The duration of exposure will then be classified into one of the following categories: > 0 Week, >= 4 Weeks, >= 8 Weeks, and >= 12 Weeks and will be presented as the number and percentage of participants in each duration category. Percentages will be computed from the number of participants in the SS.

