Dosing							
Register visit with IWRS	Х	Х	Х	Х	Х	Х	
Dispense study intervention using IWRS		Х	Х	Х			
Observe participant administer study intervention		Х					
Dispense ancillary supplies to participant		Х	Х	Х			
Participant returns unused study intervention and ancillary supplies			Х	Х	Х	Х	Where applicable as per local regulations.
Assess study intervention compliance			Х	Х	Х	Х	

Investigator; SoA = Schedule of Activities; SMBG = self-monitoring of blood glucose; T2D = Type 2 diabetes; WOCBP = women of childbearing potential. Abbreviations: BG = blood glucose; CKD-EPI = chronic kidney disease - epidemiology collaboration; CGM = continuous glucose monitoring; CRF = case report form; ECG = electrocardiogram; GLP-1 RA = glucagon-like peptide-1 receptor agonist; IWRS = interactive web-response system; PI = Principal

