### Administration and timing of dose administration

Tirzepatide is administered QW by SC injection. There are no restrictions on the time of day each weekly dose of study intervention is given, but it is advisable to administer the SC injections on the same day and same time each week, with or without meals.

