# 6.5. Dose Modification

This study is designed to assess the transition from a GLP-1 RA to tirzepatide 5 mg, and hence no dose escalation will be employed during the trial. The goal is to initiate tirzepatide at 5 mg on Visit 2 (Week 0) and maintain until Visit 5 (Week 12).

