#### Continuous blood glucose monitoring system compliance assessment

At the end of each CGM session, participants will return the CGM sensor(s) to the site. Site personnel will upload the CGM data to a vendor-hosted online portal to view data capture compliance using the available reports and visualization tools. The compliance threshold of 70% (at least 10 days of the 14-day session) for each session is defined as the percentage of actual data versus expected data collected during a session. Site personnel will re-educate participants on CGM operation and requirements when session compliance is <80%.

To minimize data loss, the CGM service vendor will review site uploads and notify site users and/or site monitor when sessions do not meet the compliance thresholds.

As noted in the SoA, if a participant does not have a compliant CGM session at Visit 3, the CGM sensor should be inserted during the study visit with re-education of the participant to ensure proper collection of this session and the subsequent CGM session prior to 12 weeks. This replacement session is not a protocol deviation, but the updated start date/time and respective study week should be documented in the CRF. The replacement CGM session data must be collected, uploaded, and assessed for compliance no later than the next study visit. A replacement CGM session is not available at Visit 5 as no additional study drug will be administered.

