6.2. Appendix 2: Treatment Compliance

Participants should administer Tirzepatide once weekly by SC injection.

Treatment overdose is defined as administration of more than a total of 3 SDPs (15mg) of Tirzepatid within a 72-hour period. If a dose is missed, the participant should take their dose as soon as possible, within 4 days (96 hours) after the missed dose. If more than 4 days have passed, that dose should be skipped, and the next dose should be taken at the appropriate time.

For each participant, study treatment compliance will be determined for each week by taking into account whether a participant takes all doses of study treatment as instructed based on the subject diary. If on a given week a participant overdosed treatment or a dose had to be skipped then that will count as non-compliance for that week. Weekly compliance along with weekly actual dose and skipped doses will be listed for each participant. Number and percentage of participants who were compliant, non-compliant (due to overdosing or due to skipping dose) will be summarized by week.

Furthermore, compliance will be characterized by accountability data for each visit. The number of SC injections taken will be calculated by subtracting the number of SDPs returned from the number of SDPs dispensed at a visit.

The study intervention compliance (%) for each visit will be calculated by dividing the total number of SDPs used up to the next visit by the total number of SDPs prescribed at each visit and then multiplying by 100. The overall study intervention compliance (%) will be calculated by dividing the total number of SDPs used at all visits by the total number of SDPs prescribed for all visits and then multiplying by 100.

Compliance (%) = [(total number of SDPs dispensed – total number of unused SDPs returned) / (Number of weeks in visit interval × Number of SDPs prescribed per week)] × 100.

Treatment compliance will be summarized descriptively. Furthermore, for overall compliance a categorical summary of whether participants were compliant (yes/no) will be presented. A participant is considered compliant if overall study intervention compliance is greater than or equal to 75%.

Percentages will be calculated out of the number of participants who were dosed at that dosing period in the Safety set.

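### SAP 4.6.1 ends exposure on the day of the last weekly injection, so an on-schedule completer of 12 doses is credited with 78 days and falls outside the 12-week category

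*SAP*

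**What the plan says.** SAP 4.6.1 defines duration of exposure as "date of last dose minus the date of first dose + 1". It reports summary statistics and four categories: "> 0 Week, >= 4 Weeks, >= 8 Weeks, and >= 12 Weeks". Missed doses are disregarded. If the last-dose date is missing, or the participant is lost to follow-up but the accountability log shows that drug was taken, "the visit date following the last completed drug accountability log will be used".

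On dosing, Protocol 6.1 states that "Tirzepatide is administered QW by SC injection". Protocol 6.5 sets the course from Week 0 to Week 12. In the Schedule of Activities (Protocol 1.3), the row "Dispense study intervention using IWRS" is marked at Visits 2, 3 and 4 only (Weeks 0, 4 and 8). Protocol 8.1.2 adds: "A replacement CGM session is not available at Visit 5 as no additional study drug will be administered". SAP 6.2 measures compliance as pens used, divided by weeks in the visit interval times the "Number of SDPs prescribed per week".

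On hypoglycaemia, SAP 4.6.4.2 counts baseline events from Week -3 to Day 1, and on-treatment events in the 14 calendar days before each of Visits 3, 4 and 5. It reports participants with an event and total events at each visit.

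**The concern.** Last dose minus first dose plus one suits a daily drug, where the last dose covers about one day. For a weekly drug it drops most of the final dosing interval. Because missed doses are disregarded, SAP 4.6.1 already treats the time between injections as exposure; only the interval after the last injection is left out. The categories, however, are whole multiples of four weeks, and the highest is the planned length of treatment.

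The exposure table of a 12-week trial could therefore show full-course participants as treated for less than 12 weeks, beside a compliance table that scores them at 100%. The fallback makes this uneven, because it ends exposure at a visit rather than at an injection.

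The by-visit hypoglycaemia summary has a similar fault in its time base. Windows of different length sit side by side, so a reader could take a difference in window length for a change in event frequency.

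**Working it through.** The plan prints no expected exposure in days, so there is no figure to reproduce. The inputs are its own rules.

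**Number of doses (assumption).** Neither document states pens per visit or total doses. Dispensing at Weeks 0, 4 and 8, no drug at Visit 5, and one pen a week in the compliance denominator imply 4 + 4 + 4 = 12.

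**Exposure on schedule.** Dose k falls on Day 1 + 7(k - 1). The SAP rule then gives an exposure equal to the day number of the last dose.

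| Doses | Day of last dose | Exposure under SAP rule | Category threshold | Exposure with + 7 |
|---|---|---|---|---|
| 4 | 22 | 22 days | 28 days | 28 days |
| 8 | 50 | 50 days | 56 days | 56 days |
| 12 | 78 | 78 days (78/7 = 11.1 weeks) | 84 days | 84 days |

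The shortfall is 84 - 78 = 6 days, or 6/84 = 7.1%. SAP 6.2 compliance for the same participant is 12/(12 × 1) = 100%.

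**Late doses.** Protocol 6.1 lets a missed dose be taken up to 4 days late. Dose 12 taken 4 days late falls on Day 82, giving 82 days, which is still below 84. Any last dose before Day 84 fails. Two 3-day shifts that carry forward put dose 12 on Day 78 + 6 = 84, which qualifies. A dose in the thirteenth weekly slot, on Day 85, gives 85 days; it needs an extra pen or one left over from a skipped dose.

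**Fallback.** SAP Table 1 places Visit 5 on Days 82 to 88. A visit date used in place of the last dose gives 82 to 88 days. Days 84 to 88 qualify, which is 5 of the 7 days.

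**Possible effect on rates.** If this duration were the denominator of a whole-period rate, the rate for an on-schedule completer would be multiplied by 84/78 = 1.077, or 7.7% too high.

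**Hypoglycaemia windows.** With visits on target Days 29, 57 and 85, the three windows are Days 15-28, 43-56 and 71-84. They cover 3 × 14 = 42 of 84 treatment days (50%) and omit Days 1-14, the first two weeks after the switch. The nominal baseline window is 21 days. At a constant event rate the count per visit relative to baseline is 14/21 = 0.667, so 33% lower with no true change. If the Schedule of Activities tolerance of +3/-7 means a screening of 18 to 28 days, and all of it is counted, the ratio runs from 14/18 = 0.78 to 14/28 = 0.50. At the 12-day minimum in Protocol 4.1.1 it is 14/12 = 1.17.

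Percentages with at least one event move in the same way. With a constant Poisson rate (assumed), 1 event per patient-year gives 5.6% over 21 days and 3.8% over 14 days; 5 per patient-year gives 25.0% and 17.4%.

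**The case against.** The 12 doses are inferred, and dosing need not stay on schedule. Protocol 6.1 only advises the same weekday and does not say that a late dose is followed by a return to it. Visits 3 to 5 carry ±3-day windows. With exactly four pens at Visit 2, a Visit 3 after Day 29 would itself delay dose 5, so either spare pens exist or doses run late. This stands: 78 days describes perfect adherence and is not a forecast. A reader might infer that nobody could reach the top category, or that 0 of 150 would. The documents do not support that, since cumulative delays or a dose on Day 85 would qualify.

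Next, the rule is openly stated, the summary statistics would show about 78 days, and compliance counts pens while exposure counts days. So this is a choice of definition, and a footnote or relabelled category would do. That is partly right: the formula is not miscalculated. But it is paired with thresholds that on-schedule weekly dosing does not meet, and a footnote would not remove the uneven fallback.

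The fallback case is uncommon. Protocol 4.1.1 requires home doses to be dated in the diary and CRF, and someone lost to follow-up would not normally have a Visit 5 date. It mainly concerns participants who attended Visit 5 with no last-dose date recorded.

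For hypoglycaemia, SAP 4.6.4.2 provides patient-year rates for severe and level 2 events, and its optional rate model has a log-months offset. These carry time denominators, so the window problem does not reach them. No test of baseline against a visit is specified, table layouts are in a separate document, and below 10 events a listing replaces the analysis.

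**Conclusion.** The point holds for the descriptive exposure outputs. Assuming 12 weekly doses, an on-schedule completer with recorded dates gets 78 days and is left out of the 12-week category; the 4- and 8-dose marks fall 6 days short in the same way. Only a last dose on or after Day 84, or the missing-date fallback, reaches the category. A participant with no last-dose date and Visit 5 on Days 84 to 88 can therefore qualify while a fully documented on-schedule completer does not.

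A reader might infer that the patient-year hypoglycaemia rates are inflated by 7.7%. That follows only if SAP 4.6.1 supplies their denominator, and the SAP does not say so. The primary HbA1c analysis, the sample size and the adverse event percentages are unaffected.

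The secondary point is confined to the by-visit hypoglycaemia counts and percentages: nominally 21 days against 14, a 33% lower count at a constant rate, with Days 1-14 absent from those windows. A reader might infer that early events are lost from the safety analysis altogether. The documents do not support this, because the incidence, rate, model and listing outputs are not stated to be limited to those windows. Both items should be corrected, but neither threatens the trial's main conclusion.

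**What to change.** Define exposure as last dose date minus first dose date plus 7. Add a footnote that this counts the weekly interval covered by the last dose and can run past the last visit. If the last-dose date is missing from the CRF disposition page, take the last dose date in the diary or dosing record and add 7. Only if none exists, keep the visit-date fallback, without adding 7, and flag those participants in the table. Do not infer doses from unreturned pens: a participant lost to follow-up returns none, and all of them would be credited as taken. State which duration is the denominator for the patient-year rates.

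For hypoglycaemia, summarise events over contiguous intervals (first dose to Visit 3, Visit 3 to 4, Visit 4 to 5, and the whole treatment period). Report baseline and on-treatment results per patient-time. Since SAP 4.6.4.2 drops events after a new antihyperglycaemic therapy starts, person-time should stop there too.

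The cost is SAP wording, table layouts and reprogramming. Dose dates and hypoglycaemic events are already collected in the diary throughout treatment, so no new data are needed.
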